Name		Degree (Program/year if student)		Position, e.g. Assistant Professor, Resident, etc.
Department	Mail Code	Phone	Fax	E-mail
CITI Training current				

Other Personnel

Participant Population(s) Checklist

Yes/No

- Children (under 18) N
- Pregnant Women and Fetuses N
- Neonates (0 - 28 days) N
- Abortuses N
- Impaired Decision Making Capacity N
- Cancer Subjects N
- Laboratory Personnel N
- Healthy Volunteers N
- Students N
- Employees N
- Prisoners N
- Other (i.e., any population that is not specified above) Y

Study Location(s) Checklist

Yes/No

- Stanford University
 - Clinical & Translational Research Unit (CTRU)
 - Stanford Hospital and Clinics
 - Lucile Packard Children's Hospital (LPCH)
 - VAPAHCS (Specify PI at VA) Y
- [name]
- Other (Click ADD to specify details)

General Checklist

Title : Skeletal Health in the Lower Limbs Following Spinal Cord Injury
Approval Period: 01/13/2015 - 09/02/2015

Multi-site**Yes/No**

- Is this a multi-site study? A multi-site study is generally a study that involves one or more medical or research institutions in which one site takes a lead role.(e.g., multi-site clinical trial)

N

Collaborating Institution(s)**Yes/No**

- Are there any collaborating institution(s)? A collaborating institution is generally an institution that collaborates equally on a research endeavor with one or more institutions.

N

Cancer Institute**Yes/No**

- Cancer-Related Studies (studies with cancer endpoints), Cancer Subjects (e.g., clinical trials, behavior/prevention) or Cancer Specimens (e.g., blood, tissue, cells, body fluids with a scientific hypothesis stated in the protocol).

N

Clinical Trials**Yes/No**

- Investigational drugs, biologics, reagents, or chemicals? N
- Commercially available drugs, reagents, or other chemicals administered to subjects (even if they are not being studied)? N
- Investigational Device / Commercial Device used off-label? Y
- IDE Exempt Device (Commercial Device used according to label, Investigational In Vitro Device or Assay, or Consumer Preference/Modifications/Combinations of Approved Devices) N
- Will this study be registered on# clinicaltrials.gov? (See Stanford decision tree) N
- Is Stanford responsible for ClinicalTrials.gov registration? (See Stanford decision tree) NCT#

Tissues and Specimens**Yes/No**

- Human blood, cells, tissues, or body fluids (tissues)? N
- Tissues to be stored for future research projects? N
- Tissues to be sent out of this institution as part of a research agreement? For guidelines, please see <https://sites.stanford.edu/ico/mtas> N

Biosafety (APB)**Yes/No**

- Are you submitting a recombinant DNA vector or Human Gene Transfer investigation using biological agents? If yes, please complete and attach the Gene Transfer Protocol Application Supplemental Questions to section 16 of the eProtocol application. N

Title : Skeletal Health in the Lower Limbs Following Spinal Cord Injury

Approval Period: 01/13/2015 - 09/02/2015

- Are you submitting a Human study using biohazardous/infectious agents? If yes, refer to the <http://www.stanford.edu/dept/EHS/prod/researchlab/bio/index.html> Administrative Panel on BioSafety website prior to performing studies. N
- Are you submitting a Human study using samples from subjects that are known or likely to contain biohazardous/infectious agents? If yes, refer to the <http://web.stanford.edu/dept/EHS/prod/researchlab/bio/index.html> Administrative Panel on BioSafety website prior to performing studies. N

Human Embryos or Stem Cells

Yes/No

- Human Embryos or Gametes? N
- Human Stem Cells (including hESC, iPSC, cancer stem cells, progenitor cells) N

Veterans Affairs (VA)

Yes/No

- The research recruits participants at the Veterans Affairs Palo Alto Health Care System(VAPAHCS). Y
- The research involves the use of VAPAHCS non-public information to identify or contact human research participants or prospective subjects or to use such data for research purposes. Y
- The research is sponsored (i.e., funded) by VAPAHCS. Y
- The research is conducted by or under the direction of any employee or agent of VAPAHCS (full-time, part-time, intermittent, consultant, without compensation (WOC), on-station fee-basis, on-station contract, or on-station sharing agreement basis) in connection with her/his VAPAHCS responsibilities. Y
- The research is conducted using any property or facility of VAPAHCS. Y

Equipment

Yes/No

- Use of Patient related equipment? If Yes, equipment must meet the standards established by Hospital Instrumentation and Electrical Safety Committee [contact]) Y
- Medical equipment used for human patients/subjects also used on animals? N
- Radioisotopes/radiation-producing machines, even if standard of care? http://www.stanford.edu/dept/EHS/prod/researchlab/radlaser/Human_use_guide.pdf More Info Y

Payment

Yes/No

- Subjects will be paid/reimbursed for participation? See payment considerations. Y

[name] will serve as a Co-Investigator and will be directly supervised by [name]. [name] has practical experience in the acquisition of kinetic and kinematic data using force plates and a multi-camera motion capture system. [name] also has prior experience working with human subjects in research. [name] will work closely with [name] to learn the basic skills involved in the handling, basic health monitoring, and general interactions with individuals with spinal cord injuries, especially during year 1 of the project. [name] has completed all required VA trainings.

Summary: The expertise and level of staffing have been carefully considered to provide appropriate skillsets and sufficient levels of effort to accomplish all of the project needs.

b) Training.

Describe the training you will provide to ensure that all persons assisting with the research are informed about the protocol and their research-related duties and functions.

The staff will read the proposal research plan and the IRB protocol and all staff will be trained regarding their specific duties and functions by [name] or his co-investigators. Staff will complete all trainings on proper research involving human subjects and on providing subject confidentiality.

c) Facilities.

Please describe and justify.

VA Palo Alto Biomotion Laboratory

The Biomotion Laboratory is a 600 square foot motion capture studio that is dedicated to the analysis of human movement for biomedical applications. The lab includes a ten-camera analysis 240 Hz Qualiys motion capture system along with two Bertec force plates mounted on a raised floor.

VA Palo Alto Bone Densitometry Facilities

Bone density measurements will be made using a Hologic QDR-1000W pencil beam DXA scanner located in the Spinal Cord Injury Unit (Bldg 7) and a Stratec XCT3000 pQCT scanner located in the

Title : Skeletal Health in the Lower Limbs Following Spinal Cord Injury
Approval Period: 01/13/2015 - 09/02/2015

Musculoskeletal Research Laboratory (Bldg. 51).

Additional laboratory space exists in Bldg. 51 to accommodate the rowing machine used for the rowing exercise sessions.

Additional office space exists in Bldg. 7 and Bldg 51 for the investigators and associated staff.

d) Sufficient time.

Explain whether you will have sufficient time to conduct and complete the research. Include how much time is required.

We believe staffing levels are sufficient given the total recruitment target of 10 individuals with SCI and the tasks to be accomplished during the two-year study.

e) Access to target population.

Explain and justify whether you will have access to a population that will allow recruitment of the required number of participants.

We expect to enroll a total of 10 participants with SCI; five individuals in a standard-of-care control group and five individuals in an FES-rowing group. Approximately 35 new patients with SCI are seen per year at the VA Palo Alto Spinal Cord Injury Center. If recruitment from VA Palo Alto proves to be insufficient, we will contact [name] who is the Chief of Spinal Cord Injury, Department of Physical Medicine & Rehabilitation, at the Santa Clara Valley (SCV) Medical Center In San Jose. [name] has agreed to provide consulting assistance as needed on the recruitment of potential participants with spinal cord injuries receiving their medical care at the SCV Medical Center. Approximately 125 new patients with SCI are seen per year at the SCI Rehabilitation Center at SCV Medical Center. Between VAPAHCS and SCV Medical Center, we do not anticipate difficulty in achieving our recruitment target.

f) Access to resources if needed as a consequence of the research.

State whether you have medical or psychological resources available that participants might require as a consequence of the research when applicable. Please describe these resources.

The VA SCI Center provides comprehensive care to patient with SCI on an in- and out-patient basis. There are dedicated physicians, nurses, therapists, and psychologists on staff with extensive experience addressing the medical and mental needs of this patient population. While it is unlikely that there will be research-related events that will require significant medical follow-up, these services are readily available within the facility.

g) Lead Investigator or Coordinating Institution in Multi-site Study.

Please explain (i) your role in coordinating the studies, (ii) procedures for routine communication with other sites, (iii) documentation of routine communications with other sites, (iv) planned management of communication of adverse outcomes, unexpected problems involving risk to participants or others, protocol modifications or interim findings.

1. Purpose

a) In layperson's language state the purpose of the study in 3-5 sentences.

Following a complete spinal cord injury (SCI), individuals experience progressive bone loss, especially in the legs, with up to 70% of persons with SCI sustaining a fracture at some point during their lifetime. Fractures following SCI are costly to treat and more than half of patients experience a medical complication, requiring extended hospitalization, resulting

Title : Skeletal Health in the Lower Limbs Following Spinal Cord Injury
Approval Period: 01/13/2015 - 09/02/2015

in a substantial impact on their quality of life. To reduce the incidence of fractures, more effective rehabilitation strategies to prevent bone loss are needed. The goal of this research is to determine if bone health can be preserved using an indoor rowing exercise program in which the leg muscles are electrically stimulated using several, small surface electrode pads that are placed on the skin on the front and back thigh muscles. An encouraging case study has recently shown remarkable bone preservation in one individual with SCI who participated in an electrical stimulation rowing program, however, whether other individuals with SCI can achieve the same benefit is currently unknown.

b) State what the Investigator(s) hope to learn from the study. Include an assessment of the importance of this new knowledge.

We hope to learn if participation in a 36-week exercise program consisting of Functional Electrical Stimulation (FES) leg muscle conditioning followed by FES-rowing can significantly attenuate bone loss in the lower limbs in individuals with acute and sub-acute SCI. Reports in the literature of attempts to prevent bone loss following SCI, via the use of anti-osteoporosis drugs, or with static loading in a standing frame, or with dynamic loading from FES-cycling have produced disappointing clinical results. If we are able to show better bone preservation than has been reported previously in a pilot group of five individuals participating in an FES-rowing program, our study will be considered a seminal and clinically important achievement.

c) Explain why human subjects must be used for this project. (i.e. purpose of study is to test efficacy of investigational device in individuals with specific condition; purpose of study is to examine specific behavioral traits in humans in classroom or other environment)

The objective of this study is to determine if participation in an FES-rowing exercise program can better preserve bone density in the lower limbs of individuals with spinal cord injury than have others types of activities or rehabilitation strategies. Previous literature studies using animals and computer models suggest that the repetitive mechanical stimulation derived from regular participation in a FES-rowing program may be sufficient to attenuate bone loss following SCI. No further animal studies or computer models can confirm the actual benefit in humans, therefore there is no other way to obtain this information without using human subjects.

2. Study Procedures

a) Please SUMMARIZE the research procedures, screening through closeout, which the human subject will undergo. Refer to sections in the protocol attached in section 16, BUT do not copy the clinical protocol. Be clear on what is to be done for research and what is part of standard of care.

In this study we expect to enroll a total of 10 participants with SCI. Five participants will be assigned to a Standard-of-Care (control) group and five participants will be assigned to an FES-rowing intervention group. Group assignment will be partly based on the preference of each potential participant and their willingness to make the necessary time commitment required for participation in a given group, with the added goal, to the extent possible, of matching the two groups for age, gender and time since injury. Only those individuals who have a strong desire to participate in a regular exercise program and who express a willingness to travel to VA Palo Alto the necessary number of times per week to perform FES-rowing will be potential candidates for inclusion in the rowing group.

Bone density measurements for both the Standard-of-Care group and the FES-rowing group will be performed using Dual energy X-ray Absorptiometry (DXA) and peripheral Quantitative Computed Tomography (pQCT). The Standard-of-Care group will undergo no other research procedures.

Title : Skeletal Health in the Lower Limbs Following Spinal Cord Injury
Approval Period: 01/13/2015 - 09/02/2015

The procedures we will use in this FES muscle strengthening and rowing program are modeled exactly after established FES-rowing research procedures in current use at Spaulding Rehab in Boston and at several research FES-rowing facilities in England. We know of no other way approaches to ask and answer the main research questions in this study.

c) State if deception will be used. If so, provide the rationale and describe debriefing procedures. Since you will not be fully informing the participant in your consent process and form, complete an alteration of consent (in section 13). Submit a debriefing script (in section 16).

Deception will not be used.

d) State if audio or video recording will occur. Describe what will become of the recording after use, e.g., shown at scientific meetings, erased. Describe the final disposition of the recordings.

Video recordings may be made while subjects perform research-related tasks, with possible use at scientific meetings. Should any videos be used during a scientific presentation the subject's face will be photographically or electronically masked to conceal their identity.

Title : Skeletal Health in the Lower Limbs Following Spinal Cord Injury
Approval Period: 01/13/2015 - 09/02/2015

All videos will be erased or destroyed after they are no longer required for use at scientific meetings. When not in use, all videos will be stored in a locked filing cabinet, in lockable office, in VA Bldg 51, which a secured building at VA Palo Alto HCS.

- e) **Describe alternative procedures or courses of treatment, if any, that might be advantageous to the participant. Describe potential risks and benefits associated with these. Any standard treatment that is being withheld must be disclosed in the consent process and form. (i.e. standard-of-care drug, different interventional procedure, no procedure or treatment, palliative care, other research studies).**

N/A

- f) **Will it be possible to continue the more (most) appropriate therapy for the participant(s) after the conclusion of the study?**

It would only be possible to continue FES-rowing using research equipment at VA Palo Alto if a follow-on research study is conducted and if a given subject continues to qualify for participation at the time of a subsequently approved study.

- g) **Study Endpoint. What are the guidelines or end points by which you can evaluate the different treatments (i.e. study drug, device, procedure) during the study? If one proves to be clearly more effective than another (or others) during the course of a study, will the study be terminated before the projected total participant population has been enrolled? When will the study end if no important differences are detected?**

The goal of this pilot study is to obtain preliminary data for five subjects participating in a 36-week FES-rowing group. Because of the small number of subjects, it is important to acquire data for all subjects and for all time points in order to determine the best estimates for key descriptive statistics including the mean, standard deviation and range of bone density changes. The study will not end until five subjects have completed the 36-week FES-rowing program.

3. Background

- a) **Describe past experimental and/or clinical findings leading to the formulation of the study.**

In 1993, Wheeler and colleagues at the University of Alberta, Canada, introduced the first functional electrical stimulation-assisted rowing system. In 1997 and in 2002, Garry Wheeler, [name], and colleagues reported refinements to the FES-rowing system and demonstrated clinically important health benefits, such as improvements in cardiovascular function. Throughout the past decade, [name] and [name] in the United Kingdom have continued to make design improvements to the rower and optimize training protocols for FES-rowing. In addition, they have been steadfast advocates for the establishment of FES-rowing programs targeting community participation and they have promoted FES-rowing competitions at international venues. Due to their efforts, FES-rowing programs now exist at four locations in the greater London area (Brunel and Coventry Universities, Aspire National Training Centre, and the London Regatta Centre). The Aspire group recently announced plans for creating additional FES-rowing facilities around the UK. Between 2007 and 2009, [name] and [name] facilitated the creation of two FES-rowing stations for installation at Spaulding Rehabilitation Hospital in Boston, MA. This effort was accomplished in collaboration with [name], Director of the Cardiovascular Research Laboratory at Harvard Medical School and Spaulding Rehab. [name] and his team have since established the Exercise for Persons with Disabilities (ExPD) program at Spaulding and

Title : Skeletal Health in the Lower Limbs Following Spinal Cord Injury
Approval Period: 01/13/2015 - 09/02/2015

ExPD has in turn recently partnered with Community Rowing Inc. to offer FES-assisted rowing systems at several locations in the Boston metropolitan area. Community Rowing also offers free rowing programs (including adapted rowing and FES-assisted rowing) to any US military service member or veteran. A similar FES-rowing program exists at the Steadward Centre for Personal & Physical Achievement at the University of Alberta. The Alberta group reports that interest in their FES-rowing program far exceeds capacity, with wait-list times of 1.5 to 3 years. These rowing programs in the UK, Alberta, and Boston have attracted many individuals with SCI who are interested in promoting health benefits via exercise and recreation, and for competition in events such as the British Indoor Rowing Championship (FES-rowing first included in 2004) and the World Indoor Rowing Championship (FES-rowing first included in 2006).

As might be expected with any sufficiently strenuous whole-body exercise regimen, FES-rowing has been reported to result in improvements in cardiovascular fitness, glucose control, and body composition. In a presentation at the 16th Annual International FES Society Conference in 2011, [name] et al. reported the only results known to date on the benefits to bone from FES-rowing, but only for a single subject. The remarkable benefit to skeletal health reported for that single individual were in large part the motivation for the present study. However, before FES-rowing can be advocated as a clinical counter-measure for bone loss following SCI we must determine if the results reported by [name] and colleagues for a single individual can be repeated in a larger pilot study. That is the goal of our study.

b) Describe any animal experimentation and findings leading to the formulation of the study.

While there are numerous studies that indicate that exercise can elicit an osteogenic response in animals, such as mice and rats, the ultimate translation of those findings must be demonstrated in humans.

4. Radioisotopes or Radiation Machines

- a) **List all standard of care procedures using ionizing radiation (radiation dose received by a subject that is considered part of their normal medical care). List all research procedures using ionizing radiation (procedures performed due to participation in this study that is not considered part of their normal medical care). List each potential procedure in the sequence that it would normally occur during the entire study. More Info**

Identify Week/Month of study	Name of Exam	Identify if SOC or Research
Start of week 0, end of weeks 8, 22 and 36	DXA and pQCT bone density measurements	Research

- b) **For research radioisotope projects, provide the following radiation-related information:**

Identify the radionuclide(s) and chemical form(s).

N/A

Title : Skeletal Health in the Lower Limbs Following Spinal Cord Injury
Approval Period: 01/13/2015 - 09/02/2015

For the typical subject, provide the total number of times the radioisotope and activity will be administered (mCi) and the route of administration.

N/A

If not FDA approved provide dosimetry information and reference the source documents (package insert, MIRD calculation, peer reviewed literature).

N/A

c) For research radiation machine projects, provide the following diagnostic procedures:

For well-established radiographic procedures describe the exam.

Bone density measurements for both the Standard-of-Care group and the FES-rowing group will be performed using Dual energy X-ray Absorptiometry (DXA) and peripheral Quantitative Computed Tomography (pQCT). These scans will take place at VA Palo Alto. Scans will be performed at four time points: baseline (time 0, i.e., at the start of week 1), and at the end of weeks 8, 22 and 36 following baseline. The DXA scans will include a proximal femur scan and a scan starting immediately proximal to the patella and extending proximally 23 cm, ending just distal to the femoral mid-shaft. Those scans will be randomized to one side only. A standard AP spine DXA scan will also be done. The pQCT scans (same side as DXA scans) will entail two image slices in the distal femur (4% and 20% up from the distal limit of the lateral femoral condyle) and three image slices in the tibia (4% and 34% down from the proximal end of the medial tibial plateau and 4% up from the distal end of the tibia, referenced from the distal limit of the tibial subchondral bone at the center of the tibiotalar joint).

For the typical subject, identify the total number of times each will be performed on a single research subject.

Each subject in each group will be scanned using DXA and pQCT on 4 occasions, at 0, 8, 22 and 36 weeks after enrollment in the study.

For each radiographic procedure, provide the setup and technique sufficient to permit research subject dose modeling. The chief technologist can usually provide this information.

Both scanners are well-established and substantial information for both exists in the literature to estimate effective dose levels.

Lewis et al. (Osteoporosis Int, 4:11-15,1994) determined effective dose (ED) levels for a hip and AP spine scans using the QDR-1000 DXA scanner. The ED for one hip scan was 0.1 microSv in males, and 1.4 microSv in females because of additional dose to the ovaries. The ED for an AP spine scan is 0.5 microSv. These dose levels were subsequently incorporated into the "Technical White Paper: Bone Densitometry" developed by the Conference of Radiation Control Program Directors' Task Force on Bone Densitometry (2006). We estimate the DXA dose for the mid-shaft/distal femur scan to be 0.1 microSv, since that scan mimic the hip scan, but with no dose to the ovaries. The total dose for the three DXA scans would be $1.4 + 0.5 + 0.1 = 2.0$ microSv. Accounting for four scan sessions throughout the study (start of week 0, end of weeks 8, 22 and 36), the total cumulative effective dose from the DXA scans would be $4 \times 2.0 = 8$ microSv.

The effective dose for the pQCT scans, based on data reported by Gordon et al. (J Bone Min Res, vol. 18, Suppl 2, p. S314, 2003), is 1.0 microSv for a single scout view plus one CT slice, with 60% of the ED, or 0.6 microSv, due to the scout view and 0.4 microSv due to the CT slice. In our protocol, we will perform 2 scout views (one at the knee; one at the ankle) and 4 CT slices (2 distal femur; 1 proximal tibia; 1 distal tibia). The total ED per scan session will be $(2 \times 0.6) + (4 \times 0.4) = 2.8$ microSv. Accounting for four scan sessions throughout the study, the total cumulative effective dose from the pQCT scans will be $4 \times 2.8 = 11.2$ microSv.

The combined total effective dose from all DXA scans and all pQCT scans will be 19.2 microSv, which is slightly more than 2 days of background radiation based on an average background radiation dose of 3,000 microSv per year in the US (Report in Brief, June 2005, BEIR VII: Health Risks from Exposure to Low Levels of Ionizing Radiation, National Research Council).

For radiographic procedures not well-established, provide FDA status of the machine, and

Title : Skeletal Health in the Lower Limbs Following Spinal Cord Injury
Approval Period: 01/13/2015 - 09/02/2015

information sufficient to permit research subject dose modeling.

Both radiographic procedures (DXA, pQCT) are well-established and both scanners are FDA approved.

d) For research radiation machine projects, provide the following therapeutic procedures:

For a well-established therapeutic procedure, identify the area treated, dose per fraction and number of fractions. State whether the therapeutic procedure is being performed as a normal part of clinical management for the research participants' medical condition or whether it is being performed because the research participant is participating in this project.

N/A

For a therapeutic procedure that is not well-established, provide FDA status of the machine, basis for dosimetry, area treated, dose per fraction and number of fractions.

N/A

5. Devices

a) Please list in the table below all Investigational Devices (including Commercial Devices used off-label) to be used on participants.

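### The aim is worded as showing significant and better bone preservation, but the only analysis named is descriptive, with no interval and no rowing–control contrast

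*Combined protocol and SAP*

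**What the plan says.** Section 1(b) says the investigators hope to learn whether the 36-week programme "can significantly attenuate bone loss in the lower limbs in individuals with acute and sub-acute SCI". It adds that the study will count as a seminal result if they can "show better bone preservation than has been reported previously in a pilot group of five individuals" taking part in FES-rowing. Section 1(c) sets the objective as whether rowing "can better preserve bone density in the lower limbs of individuals with spinal cord injury than have others types of activities or rehabilitation strategies".

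Section 2(g), on the study endpoint, states a more modest goal: "The goal of this pilot study is to obtain preliminary data for five subjects participating in a 36-week FES-rowing group". It stresses complete data because numbers are small, the purpose being to "determine the best estimates for key descriptive statistics including the mean, standard deviation and range of bone density changes".

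The section on access to the target population gives the size: "five individuals in a standard-of-care control group and five individuals in an FES-rowing group". Section 4(c) has every subject in both groups scanned by DXA and pQCT at 0, 8, 22 and 36 weeks. Section 2(a) says assignment depends partly on preference, with matching on age, gender and time since injury where possible. Section 8(h) sets different eligibility by group, including injury level: T1 to T12 for rowers and C5 to T12 for controls.

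The document contains no confidence interval, test, significance level, rowing–control contrast, primary bone site or numerical meaning for better.

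**The concern.** The aim and the analysis do not match. Words such as significantly and better call for an estimate with its uncertainty. A mean, SD and range can be reported without showing any. The comparison with earlier strategies has no stated form, and the concurrent controls have no stated role, although they are scanned on the same schedule.

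Two things are at stake. A favourable average in five rowers could be presented as an answer to the aim when the data are compatible with a wide range of true effects. And the SD of change, which a pilot commonly passes on to the next trial's sample-size calculation, could be quoted with no sign of how loosely it is known.

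**Working it through.** **Inputs.** Five rowers and five controls (access to target population; section 2(a)). Scans at baseline and three follow-ups in both groups (section 4(c)). Descriptive statistics of change (section 2(g)). The document gives no SD, significance level, effect size or benchmark, so there is no figure of the plan's own to reproduce. Results below are in multiples of the observed SD of change. They assume a 95% level, roughly normal changes, and week-36 data on all five subjects in each group.

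**1. Mean change in the rowers.** Half-width = t(0.975, 4)/√5 = 2.776/2.236 = **1.24 SD**.

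**2. Rowing minus control.** Half-width = t(0.975, 8) × √(1/5 + 1/5) = 2.306 × 0.6325 = **1.46 SD**, using a pooled SD and so assuming equal variances.

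**3. SD of change in one group (4 df).** The limits are √(4/χ²) times the estimate:
- lower: √(4/11.14) = **0.60**
- upper: √(4/0.4844) = **2.87**

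The upper limit is nearly five times the lower.

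**4. SD pooled over both groups (8 df).** Under equal variances:
- lower: √(8/17.53) = **0.68**
- upper: √(8/2.180) = **1.92**

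This is tighter, but equal variances cannot be taken for granted when eligibility differs by group.

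**5. What a test could detect.** If significantly were taken literally as a two-sided 5% t-test of 5 against 5 (an assumption; the plan names no test), the noncentral t distribution gives 29% power for a true difference of 1 SD. A difference of about 2.02 SD is needed for 80%.

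**6. Why one site must be named.** Section 4(c) describes three DXA regions and five pQCT slices, eight in all, at three follow-ups. Suppose any of eight 95% intervals lying wholly on rowing's side of zero were taken as a success. With no true effect and independent sites, the chance of at least one at a given time point is 1 − 0.975⁸ = 0.18. Positive correlation between sites would lower this.

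**The case against.** The strongest defence is that this is a pilot and says so. Section 1(b) speaks of what the investigators hope to learn, section 2(g) speaks of preliminary data, and descriptive statistics are a sound choice for five plus five. That stands. The defect is the wording of the aim, together with the missing intervals and contrast; it is not the choice to describe.

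It can also be said that the list in 2(g) is open-ended, that the form asks applicants not to copy the clinical protocol, and that section 16 lists an attached VA proposal that may hold an analysis plan. This also stands, so the point is limited to this document. If the proposal does contain such a plan, 2(g) should cite it. Finally, a reader could build a one-group interval from a mean, SD and n. That shows how cheap the fix is, but it does not define the contrast or the site.

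Three stronger readings are tempting, and the documents do not support them.

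- *Rowing will be declared better whenever its mean is larger, so half the time under no effect.* No such rule is stated. The 50% is true of any symmetric estimate at any sample size. It also fails here if preference-based assignment shifts the expected difference: a shift of −0.5 or +0.5 SD gives 21% or 79%.
- *The SD will come from the rowers alone.* The goal sentence in 2(g) names the five rowers, but the sentence on statistics refers to data for all subjects. The role of the controls is unstated; they are not excluded.
- *A rowing–control interval that excludes zero would justify saying better.* Sections 1(b) and 1(c) compare with earlier published strategies, which a concurrent contrast does not address. Such a rule would also meet the multiplicity in step 6. Nor would a permutation p-value have a randomisation basis here.

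**Conclusion.** The point holds as a mismatch between the aim and the only analysis named in this document. With five per group, the mean change in rowers is known to about ±1.24 SD and the difference from controls to about ±1.46 SD. A single-group SD is known only to within 0.60 to 2.87 times its estimate. These figures rest on approximate normality and complete week-36 data, and the ±1.46 SD also on equal variances. They cover sampling error only. They do not cover selection from preference-based assignment and differing eligibility, or differences between these rowers and the subjects of published studies.

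The study can give useful preliminary estimates. It cannot be expected to settle whether rowing significantly attenuates loss, or is better, unless the effect is very large. This is a worthwhile and inexpensive improvement; it is not a flaw that invalidates the pilot.

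**What to change.** **Section 2(g).** Name one lower-limb site in advance and use the change from baseline to week 36. For that outcome, report:

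1. the rowing group's mean change with its 95% t interval, for comparison with published results;
2. the rowing-minus-control difference in mean change with its 95% t interval, labelled non-randomised because assignment is partly by preference and eligibility differs by group;
3. the SD of change in each group with its 95% interval, adding a pooled SD on 8 df only under a stated equal-variance assumption.

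Treat all other sites and time points as descriptive.

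**Sections 1(b) and 1(c).** Replace the wording about significant attenuation and about determining whether rowing is better with an aim to estimate, with 95% intervals, the change in bone density during the programme and its difference from concurrent controls. State that the comparison with earlier strategies is informal.

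**Cost.** A few lines of text and analysis, with no added subjects, visits or scans. The downside is that the stated claim becomes less favourable.
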